6.4.3. Lenalidomide Administration

Lenalidomide will be provided in accordance with the Revlimid REMS® program of Celgene Corporation. Per standard Revlimid REMS® requirements, all physicians who prescribe lenalidomide for research subjects enrolled into this trial must be registered and must comply with all requirements of the Revlimid REMS® program. Prescriptions must be filled within 7 days.

Subjects will receive lenalidomide as follows in 28-day cycles:

- Cycle 1-8: 25 mg days 1-21
- Cycles 9+: best tolerated dose days 1-21

Lenalidomide should be taken each evening at approximately the same time. Lenalidomide is taken with water on a full or empty stomach. Subjects should not break, chew or open capsules. Late doses of Lenalidomide should if possible be taken on the assigned day but should not be made up the next day. Vomited doses will not be made up. Subjects should be instructed to never take Lenalidomide past Day 21 of each cycle.

6.4.4. Dexamethasone Administration

Dexamethasone will be administered no longer than 3 hours preceding elotuzumab and between 30 min and 4 hours prior to carfilzomib (on days that they coincide). When dexamethasone, carfilzomib and elotuzumab coincide, dexamethasone will be given first, followed by carfilzomib and finally elotuzumab will be infused:

- Cycle 1-2: 20 mg IV not longer than 3 hours prior to elotuzumab infusion and between 30 min and 4 hours prior to carfilzomib on Days 1, 8, and 15. 20mg PO will be taken on Days 2, 9, and 16 and 40mg PO will be taken as a single dose on Day 22 not longer than 3 hours prior to elotuzumab infusion.
- Cycles 3-4: 40 mg PO Days 1, 8, 15, 22. On days when dexamethasone coincides with elotuzumab, dexamethasone will be taken no longer than 3 hours prior to elotuzumab infusion. On days when carfilzomib is given, dexamethasone will be dosed between 30 min and 4 hours prior to carfilzomib
- Cycles 5+: 20mg PO Days 1, 8, 15, 22. On days when dexamethasone coincides with elotuzumab, dexamethasone will be taken not longer than 3 hours prior to elotuzumab infusion. On days when carfilzomib is given, dexamethasone will be dosed between 30 min and 4 hours prior to carfilzomib

Split weekly dosing on cycles other than cycle 1 (e.g. 10mg on Day 1 and 10mg on Day 2, etc.) is permitted with approval from Lead Principal Investigator

Dexamethasone given on days without elotuzumab or carfilzomib (on cycles 3+ day 22) may be self-administered by the subject on an outsubject basis.

Missed doses of dexamethasone will not be made up.

6.4.5. Maintenance treatment

Subjects that complete 12 cycles (who were MRD-negative after cycles 8 and 12), 18 cycles (who were MRD-positive after cycle 8 but MRD-negative after cycle 12), or 24 cycles (who were MRD-positive after cycle 8 and 12) of E-KRd, will continue a regimen of E-Rd until disease progression. This regimen will have elotuzumab every four weeks, lenalidomide at best-tolerated dose (days 1-21), and low dose dexamethasone (weekly) in 28-day cycles until disease progression.

6.4.6. Treatment Compliance

Research center personnel will review the dosing instructions with subjects. Subjects will be asked to maintain a diary to record drug administration. Subjects will be asked to bring empty drug containers to the research center at their next visit for destruction.

6.5. Instructions for Initiation of a New Cycle

A new course of treatment may begin on the scheduled Day 1 of a new cycle if all of the following are met:

- ANC $> 1.0 \times 10^9/L$
- Platelet count $\geq 30 \times 10^9/L$
- Any other study drug-related adverse event must have resolved to grade 1 or baseline (see Appendix 2)
- Serum uric acid and creatinine concentrations must return to baseline prior to carfilzomib doses during Cycles 1 and 2

If these conditions are not met on Day 1 of a new cycle, the subject will be evaluated weekly, and a new treatment cycle will not be initiated until the toxicity has resolved, as described above.

If elotuzumab, carfilzomib or lenalidomide are held for the remainder of the previous cycle or the new cycle is delayed due to residual toxicity on the planned Day 1 of the next cycle, then the new cycle will be started at 1 dose decrement.

If a delay of starting a new cycle is greater than 21 days, the subject should be discontinued from treatment, unless continuing treatment is mutually agreed upon by the site Lead Principal Investigator at the University of Chicago and the Co-Investigator at the treating institution.

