Tumor lysis syndrome (≥ 3 of the following: ≥ 50% increase in creatinine, uric acid, or phosphate;≥ 30% increase in potassium;≥ 20% decrease in calcium; or ≥ 2-fold increase in LDH	Hold lenalidomide until all abnormalities in serum chemistries have resolved. Reinstitute at full doses.	Hold carfilzomib until all abnormalities in serum chemistries have resolved. Reinstitute at full doses.	Hold Upon resolution elotuzumab can be restarted at the treating physician's discretion		
Infection Grade 3 or 4	Hold lenalidomide until systemic treatment for infection is completed. If no neutropenia, restart lenalidomide at full dose. If neutropenic, follow neutropenic instructions.	Hold carfilzomib until systemic treatment for infection is completed If no neutropenia, restart carfilzomib at full dose. If neutropenic, follow neutropenic instructions.	Hold Upon resolution elotuzumab can be restarted at the treating physician's discretion		
Herpes zoster or simplex of any grade	Hold lenalidomide until lesions are dry. Reinstitute at full doses.	Hold carfilzomib until lesions are dry. Reinstitute at full doses.	Hold When lesions are dry elotuzumab can be restarted at the treating physician's discretion		
Grade 2 neuropathy with pain or any Grade 3 neuropathy	Hold until ≤ Grade 2. Then restart lenalidomide at 1 dose decrement	Withhold until toxicity is resolved or returned to baseline After resolution, consider if restarting CFZ at the same dose or at a reduced dose is appropriate. If tolerated, the reduced dose may be escalated to the previous dose at the discretion of the physician	Hold Upon resolution elotuzumab can be restarted at the treating physician's discretion		
Grade 4 neuropathy	Discontinue	Discontinue	Hold Upon resolution elotuzumab can be restarted at the treating physician's discretion		
Renal dysfunction					
Serum creatinine > 2 mg/dL	Base dose reduction on calculated GFR (below)	Base dose reduction on calculated GFR (below)	Hold Upon resolution elotuzumab can be		

Table 6-6 Dose Modifications for Non-hematologic Toxicity

	Recomme	nded Action	
Non-heme toxicity	Lenalidomide	Carfilzomib	Elotuzumab
			restarted at the treating physician's discretion
CrCl>60 mL/min	Full dose	Full dose	Full dose
CrCl <60 mL/min > 30 mL/min	Reduce lenalidomide to 10 mg every 24 h; may reinstate prior dose if, after 2 cycles, CrCl normalizes	Full dose	Full dose

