6.10.3. Tumor Lysis Syndrome

TLS, which may be associated with multi-organ failure, has been observed in treatment Cycles 1 and 2 in some subjects with MM who have been treated with carfilzomib. All subjects should follow the hydration guidelines outlined in Section 6.3.2. If subjects are considered to be at risk for TLS, hydration should be continued into Cycle 2 if clinically indicated.

MM subjects with high tumor burden (e.g., Durie-Salmon or ISS Stage II/III), rapidly increasing M-protein or light chains, or compromised renal function (CrCl < 50 mL/min) should be considered to be at particularly high risk.

During Cycles 1 and 2, serum electrolytes and chemistries are closely monitored. Subjects with laboratory abnormalities consistent with lysis of tumor cells (e.g. serum creatinine $\geq 50\%$ increase, LDH \geq 2-fold increase, uric acid $\geq 50\%$ increase, phosphate $\geq 50\%$ increase, potassium $\geq 30\%$ increase, calcium $\geq 20\%$ decrease) prior to dosing should not receive the scheduled dose. Subjects with such abnormalities should be re-evaluated as clinically indicated. The Lead Principal Investigator should be consulted if there are further delays.

If TLS occurs, cardiac rhythm, fluid, and serial laboratory monitoring should be instituted. Correct electrolyte abnormalities, monitor renal function and fluid balance, and administer therapeutic and supportive care, including dialysis, as clinically indicated.

All cases of TLS must be reported to the Lead Principal Investigator (who will, in turn be responsible for distributing this information to all sites) and to Amgen as a Serious Adverse Event (SAE) through the normal process within 24 hours of the clinical site becoming aware of the event.

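### Section 6.5, section 6.10.3 and Table 6-6 set different, unranked laboratory triggers for holding carfilzomib in Cycles 1-2, and they conflict directly on the restart dose and on dosing when creatinine exceeds 2 mg/dL

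*Combined protocol and SAP*

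**What the plan says.** Section 6.5 introduces its conditions with "A new course of treatment may begin on the scheduled Day 1 of a new cycle if all of the following are met". The last of them reads "Serum uric acid and creatinine concentrations must return to baseline prior to carfilzomib doses during Cycles 1 and 2". It names two analytes and gives no margin. If the conditions fail, the subject is re-evaluated weekly and the cycle waits. A cycle delayed for residual toxicity then starts one dose level lower.

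Section 6.10.3 covers the same two cycles: "During Cycles 1 and 2, serum electrolytes and chemistries are closely monitored". It says that "Subjects with laboratory abnormalities consistent with lysis of tumor cells" (examples: creatinine, uric acid or phosphate up by at least 50%, LDH at least doubled, potassium up by at least 30%, calcium down by at least 20%) "prior to dosing should not receive the scheduled dose". It states no minimum number of abnormalities and no restart dose.

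The tumor lysis row of Table 6-6 (section 6.6.1.2) begins "Tumor lysis syndrome (≥ 3 of the following: ≥ 50% increase in creatinine, uric acid, or phosphate" and continues with the same potassium, calcium and LDH cut-offs. It is not limited to Cycles 1-2. Its carfilzomib instruction is "Hold carfilzomib until all abnormalities in serum chemistries have resolved. Reinstitute at full doses".

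The renal rows of the same table say that, once serum creatinine exceeds 2 mg/dL, dosing follows calculated clearance. Carfilzomib is given at full dose for CrCl between 30 and 60 mL/min and held below 30.

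**The concern.** Chemistry must be reviewed before every carfilzomib dose in these two cycles (sections 6.4.2 and 6.10.4), so each site has to apply a rule to the result. It can reach a different decision depending on the section it opens. This is the period in which section 6.10.3 reports tumor lysis, and section 6.10.2 describes a creatinine rise on Day 2 after the first dose.

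The consequences reach beyond one visit. Missed carfilzomib doses are not replaced within a cycle (section 6.4.2). A new-cycle delay of more than 21 days means discontinuation unless the investigators agree otherwise (section 6.5). The restart dose also differs by section. Safety handling and dose delivery in the step-up phase could therefore vary between the five centers for reasons unrelated to the subjects.

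The pointers add to the difficulty. For renal guidance, section 6.4.2 sends the reader to Table 6-1, which holds dose levels, and section 6.10.4 to Table 6-7. The renal rows stand in Table 6-6.

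**Working it through.** No sample size, power or alpha figure is involved, so there is no plan figure to reproduce. The check applies the rules to the same laboratory results.

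**1. The three triggers side by side.** The 6.5 column uses only the uric acid and creatinine condition. Section 6.10.3 is read as met by any one listed abnormality. The tumor lysis row counts each of the six analytes separately. Analytes not named are at baseline.

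| Pre-dose result against baseline | 6.5 | 6.10.3 | Table 6-6, tumor lysis row |
|---|---|---|---|
| Creatinine +20% | hold | silent | silent |
| Uric acid +40% | hold | silent | silent |
| Creatinine +60% | hold | hold | silent |
| Creatinine and uric acid +60% | hold | hold | silent |
| Potassium +35% | silent | hold | silent |
| Potassium +35%, phosphate +60%, calcium -25% | silent | hold | hold |
| Creatinine, uric acid, phosphate +60% | hold | hold | hold |

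The triggers differ in 6 of these 7 results. If 6.10.3 is read as needing two abnormalities, the potassium-only case becomes silent in all three columns, and 5 of 7 still differ. The cases were chosen to separate the rules, so neither count is a frequency. Silent means that the rule is not triggered; it is not an instruction to dose.

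**2. Scope of the 6.5 condition.** Read as a Day 1 condition, it gates only Cycle 2 Day 1. Read by its own words on carfilzomib doses in both cycles, it gates Cycle 1 Days 8 and 15 and Cycle 2 Days 1, 8 and 15. The text supports either reading.

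**3. Restart dose.** Suppose Cycle 2 Day 1 is delayed for tumor lysis that then resolves.
- Scheduled carfilzomib dose from Cycle 2 (section 6.4.2): 70 mg/m².
- Section 6.5: one level lower. By the carfilzomib Table 6-1 that is 56 mg/m².
- Tumor lysis row: full dose, 70 mg/m².
- Difference: 1 - 56/70 = 0.20, or 20%.

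Both instructions cannot be followed.

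**4. Renal rows.** Inputs: the Cockcroft-Gault formula in section 5.1 and an assumed man of 65 years and 80 kg whose creatinine rises from 1.0 to 2.1 mg/dL.
- Rise: 2.1/1.0 - 1 = 110%.
- CrCl = (140 - 65) × 80 / (72 × 2.1) = 6000/151.2 = 39.7 mL/min.
- 6.5: not at baseline, withhold. 6.10.3: rise of at least 50%, withhold. Tumor lysis row: one abnormality, not triggered. Renal row: full dose.

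At 2.1 mg/dL, men aged 50, 65 or 75 years weighing 60, 80 or 100 kg have CrCl from 25.8 to 59.5 mL/min. Seven of these nine combinations fall between 30 and 60. If the baseline were 1.5 mg/dL the rise would be 2.1/1.5 - 1 = 40%, below the 6.10.3 cut-off, and only 6.5 would oppose the renal row.

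**5. Calcium.** A calcium fall is a trigger in both 6.10.3 and the tumor lysis row. The chemistry panels listed in sections 6.2.1 and 6.2.2 and in Appendix 6, footnote 9, do not include calcium.

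**The case against.** The strongest reply is that the three passages do different jobs and can all be applied at once. Section 6.5 governs the start of a cycle, 6.10.3 is a pre-dose precaution, and the tumor lysis row defines an event and its management. A lower precautionary threshold beside a higher event definition is no contradiction in itself. This largely stands. A reader might infer that the three triggers alone make the same result both dosed and withheld. The documents do not support that: each is a hold rule, and none directs dosing when its own trigger is not met. Nor does the tumor lysis row let single marked abnormalities through on its own, because 6.10.3 and the required chemistry review still apply and section 6.6 lets the investigator hold treatment.

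A reader might also infer that 6.5 costs many doses through chance variation around baseline. The documents give no data on that variation. They also leave open whether more than one dose is gated, and a failed Day 1 delays a cycle; it does not forfeit it.

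On the restart, it can be said that the specific tumor lysis row overrides the general rule, and that 70 mg/m² is itself a planned escalation from 56, given if tolerated. That is reasonable, but no precedence is written down. On the renal rows, it can be said that they set only the dose level for subjects otherwise fit to be dosed. But the neighboring row for CrCl below 30 orders a hold, so these rows also decide whether carfilzomib is given.

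**Conclusion.** The concern holds as an internal inconsistency in the rules for carfilzomib in Cycles 1-2. The laboratory triggers differ, nothing ranks them, and the reach of the 6.5 condition is ambiguous between one dose and five. Two instructions cannot both be followed:
- The restart after a Cycle 2 Day 1 delay for tumor lysis: 56 or 70 mg/m², taking 70 as the scheduled dose.
- Dosing at creatinine above 2 mg/dL with CrCl 30-60 mL/min: full dose or withhold. The 39.7 mL/min example rests on the assumed age, weight and creatinine values. In the age and weight grid the conflict arises in most combinations, not all.

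How often either situation would occur cannot be estimated from the documents. The finding does not touch the primary test or its error rates. It is worth correcting because it bears on subject safety and on uniform dose delivery. No judgment is made on which threshold or dose is right.

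**What to change.** The sponsor should reconcile section 6.5, section 6.10.3 and the tumor lysis and renal rows of Table 6-6 so that together they state:
- one consistent pre-dose laboratory rule for carfilzomib in Cycles 1-2, including how many abnormalities are needed;
- which doses in those cycles the rule covers;
- one restart instruction after a hold or a delayed cycle;
- cross-references, so that each passage leads to the same rule.

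The same amendment should correct the renal pointers in sections 6.4.2 and 6.10.4 and reconcile the calcium trigger with the listed chemistry panel. The choice of thresholds and doses rests with the sponsor.

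The cost is a wording amendment. Creatinine, uric acid, phosphorus, potassium and LDH are already in the pre-dose panel. Calcium is the one item that may need more than wording, if the sponsor keeps it as a trigger.

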6.6. Dose-Modification Guidelines

The following sections and tables summarize dosing modifications of elotuzumab, carfilzomib, lenalidomide, and dexamethasone to manage possible toxicity. Dose modifications different from those stated in the protocol should be discussed with the Lead Principal Investigator. Administration of carfilzomib and lenalidomide will be discontinued in the event of any other toxicity that, in the opinion of the Lead, Secondary Site, or Treating Investigator, warrants discontinuation.

In addition to dose reductions, administration of elotuzumab, carfilzomib and lenalidomide will be held temporarily in the event of a treatment-related toxicity at the Treating Investigator's discretion. Study treatment may be reintroduced if resolution of the event to the baseline value or to \leq Grade 1 within 21 days; otherwise study drug will be permanently discontinued. Any deviations from this plan must be approved by the Lead Principal Investigator.

If a subject's elotuzumab administration is delayed on day 1 of a cycle, carfilzomib, lenalidomide, and dexamethasone will also be delayed until the elotuzumab is resumed, which would then become the new day 1 of that cycle.

If a subject's elotuzumab is held in the middle of a cycle, carfilzomib, dexamethasone, and lenalidomide dosing will continue as scheduled. If the subject's elotuzumab is delayed during the cycle and is resumed within the designated window, (+/-3 days Cycles 1 and 2; +/-7 days Cycles 3 and beyond) the subject may receive the scheduled dose. If the elotuzumab is not resumed within the given window (+/-3 days Cycles 1 and 2; +/-7 days Cycles 3 and beyond), the subject is to omit that dose, and resume dosing at the next dosing time point.

If a study drug (except dexamethasone) is discontinued, the subject may continue on trial. However, if the discontinuation happens prior to the end of cycle 8 (1^{ary} endpoint), the subjects will Page 45

continue to be treated and will only be included on the intent to treat analysis.

All clinically-significant non-hematologic toxicities must be resolved to Grade 1 or baseline.

Dose reduction levels of elotuzumab, carfilzomib, lenalidomide, and dexamethasone for toxicity management of individual subjects are provided below:

Table 6-1 Carfilzomib Dose Adjustments

Nominal carfilzomib dose	Dose -1	Dose -2	Dose -3	Dose -4
70 mg/m^2	56 mg/m^2	45 mg/m^2	36 mg/m^2	27 mg/m^2

Table 6-1 Lenalidomide Dose Adjustments

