Nominal Lenalidomide Dose	Dose -1	Dose -2	Dose -3
25 mg Days 1-21	15 mg	10 mg	5 mg

Table 6-3 Dexamethasone Dose Adjustments

Nominal Dexamethasone Dose	Dose -1	Dose -2	Dose -3
40mg or 20 mg	Reduce dexamethasone by 50% from starting dose; however, the 20-mg IV dose of dexamethasone given before the infusion on the day of elotuzumab infusions must not be decreased.	dexamethasone on the day when elotuzumab is	Discontinue dexamethasone

^{*}Split dosing of dexamethasone on days 1,2, 8,9, 15,16, 22,23 may be implemented to control toxicities that do not require a dose reduction. Split dosing requires the approval of the Lead Principal Investigator

6-4 Elotuzumab Dose Adjustments

No dose reductions for elotuzumab are allowed. If Elotuzumab is held on Day 1 of a new cycle, treatment with carfilzomib/lenalidomide/dexamethasone will also be delayed. If elotuzumab is held during any cycle on days 8, 15, or 22, the treating investigator will decide if lenalidomide, carfilzominb, and/or dexamethasone will be held using recommended guidance for retreatment below. Treatment may be delayed for a maximum of 21 days (see section 6.5.2.1 for details).

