Other non-hematologic toxicity assessed as lenalidomide-related ≥ Grade 3	Hold lenalidomide dose. Follow at least weekly. If the toxicity ≤ Grade 1 before Day 21 of the current cycle, restart at 1 dose decrement and continue until Day 21 of the current cycle	Full dose	Full dose

Table 6-6 Dose Modifications for Non-hematologic Toxicity

Recommended Action			
Non-heme toxicity	Lenalidomide	Carfilzomib	Elotuzumab
Other non-hematologic toxicity assessed as carfilzomib-related ≥ Grade 3	Full dose	Hold carfilzomib dose until toxicity resolves to ≤ Grade 1 or baseline. After resolution, consider if restarting CFZ at the same dose or at a reduced dose as appropriate. If tolerated, the reduced dose may be escalated to the previous dose at the discretion of the physician.	Full dose
Other non-hematologic toxicity assessed as elotuzumab-related ≥ Grade 3	Full dose	Full dose	Hold Upon resolution, restart at the treating physician's discretion
Other non-hematologic toxicity assessed as drug- related ≥ Grade 3	Hold treatment and restart at 1 dose decrement when toxicity has resolved to ≤ Grade 1 or baseline	Hold treatment and restart at 1 dose decrement when toxicity has resolved to ≤ Grade 1 or baseline	Hold treatment and restart when toxicity has resolved to ≤ Grade 1 or baseline

Table 6-8 Dose Modification Guidelines for Toxicity Related to Dexamethasone

BODY SYSTEM	SYMPTOM	RECOMMENDED ACTION	
Gastrointestinal	Dyspepsia, gastric or duodenal ulcer, gastritis Grade 1-2 (requiring medical management)	Treat with H2 blockers, sucralfate, or omeprazole. If symptoms persist despite above measures, decrease dexamethasone dose by 1 dose level.	
Gastrointestinal	≥ Grade 3 (requiring hospitalization or surgery)	Hold dexamethasone until symptoms adequately controlled. Restart at 1 dose decrement along with concurrent therapy with H2 blockers, sucralfate, or omeprazole. If symptoms persist despite above measures, discontinue dexamethasone permanently.	
Gastrointestinal	Acute pancreatitis	Discontinue dexamethasone permanently.	
Cardiovascular	Edema ≥ Grade 3 (limiting function and unresponsive to therapy or anasarca)	Diuretics as needed, and restart dexamethasone at 1 dose decrement; if edema persists despite above measures, decrease dose another level Discontinue dexamethasone permanently is symptoms persist despite second reduction.	
Neurology	Confusion or mood alteration	Hold dexamethasone until symptoms resolve. Restart at 1 dose decrement. If symptoms	

UCM IRB 16-1138

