If a subject with a prior Grade 2-3 infusion reaction also requires dose reduction of dexamethasone, the weekly dexamethasone on the days of elotuzumab infusion should be no lower than 8 mg IV (on the day of elotuzumab infusion at least 45 minutes prior to elotuzumab). Subjects with a Grade 4 elotuzumab infusion reaction must have elotuzumab permanently discontinued. Additionally, subjects who have a recurrence of \geq Grade 2 infusion reactions with subsequent doses and subjects who have a true hypersensitivity reaction at \geq Grade 2 should have elotuzumab permanently discontinued (but may continue on KRd).

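### Section 6.5 orders a one-level dose reduction after an elotuzumab hold or a Day 1 delay without naming the drug, although elotuzumab has no dose levels and Table 6-6 gives different restart doses for some of the same events

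*Combined protocol and SAP*

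**What the plan says.** Section 6.5 sets the conditions for starting a new cycle. Besides blood count limits, "Any other study drug-related adverse event must have resolved to grade 1 or baseline". It then gives a mandatory rule with two triggers: "If elotuzumab, carfilzomib or lenalidomide are held for the remainder of the previous cycle or the new cycle is delayed due to residual toxicity". The second trigger is assessed at the scheduled start of the cycle. In either case "then the new cycle will be started at 1 dose decrement". No drug is named as the one to be reduced.

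Section 6.6 introduces reduction levels for all four drugs. The tables give carfilzomib 70 mg/m2 with a first reduction to 56 mg/m2, and lenalidomide 25 mg with a first reduction to 15 mg. For elotuzumab, item 6-4 says "No dose reductions for elotuzumab are allowed".

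If elotuzumab is delayed on Day 1 of a cycle, "carfilzomib, lenalidomide, and dexamethasone will also be delayed until the elotuzumab is resumed". No reduction is mentioned there. After a mid-cycle elotuzumab hold, 6.6 and 6.6.2.1 keep the partner drugs on schedule.

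In Table 6-6, the row headed "Other non-hematologic toxicity assessed as elotuzumab-related" (Grade 3 or more) lists full dose for lenalidomide and for carfilzomib, and a hold for elotuzumab. Section 6.6.2 lets subjects who stop elotuzumab after recurrent or hypersensitivity reactions stay on KRd, again with no reduction mentioned.

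**The concern.** The 6.5 rule names elotuzumab as a trigger, but the action it orders cannot be carried out on elotuzumab. A site has to decide for itself whether the rule is void in that case or falls on the backbone drugs. Two sites can follow the protocol in good faith and dose carfilzomib and lenalidomide differently after the same event.

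At stake is the dosing of the KRd backbone, and its consistency across the 5 centers (Section 4.2.2), before the cycle 8 assessment that defines the primary endpoint.

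**Working it through.** The plan states no figure on this point. The check is a comparison of rules, followed by the size of one dose step.

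**1. Can elotuzumab toxicity alone reach the triggers?** Yes, both of them.
- Hold for the rest of a cycle: from cycle 3, elotuzumab is given only on days 1 and 15 (4.2, 6.4.1). A day 15 dose that is not resumed within the 7-day window of 6.6 is omitted, and the next dose is Day 1 of the following cycle. One omitted dose is thus a hold for the remainder of the cycle.
- Day 1 delay: 6.5 requires any study-drug-related event to have settled, so an unresolved elotuzumab-related event delays the cycle. Section 6.6 then delays the partners with it.

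**2. What does 6.5 then order, compared with the specific rules?**

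| Event | Section 6.5 | Specific rule |
|---|---|---|
| Other elotuzumab-related toxicity, Grade 3 or more | one level down, drug not named | Table 6-6: lenalidomide and carfilzomib at full dose |
| Tumor lysis syndrome delaying Day 1 | one level down, drug not named | Table 6-6: both restart at full dose |
| Grade 3 or 4 infection without neutropenia delaying Day 1 | one level down, drug not named | Table 6-6: both restart at full dose |
| First platelet fall below 30 x 10^9/L delaying Day 1 | one level down, drug not named | Table 6-5: carfilzomib at previous dose, lenalidomide one level down |

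No text in the document says which rule prevails.

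**3. Size of one step, if a partner is reduced from full dose in one of cycles 2 to 8.**
- Carfilzomib: 3 x 70 = 210 against 3 x 56 = 168 mg/m2. The loss is 42, and 42/210 = 20%.
- Lenalidomide: 21 x 25 = 525 against 21 x 15 = 315 mg. The loss is 210, and 210/525 = 40%.
- Under the elotuzumab-related row of Table 6-6, the change is 0% for both.

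**4. Share of the planned dose over cycles 1 to 8, one affected cycle.**
- Planned carfilzomib: 20 + 56 + 56 + 7 x 210 = 1602 mg/m2. Share lost: 42/1602 = 2.6%.
- Planned lenalidomide: 8 x 525 = 4200 mg. Share lost: 210/4200 = 5.0%.

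Since 6.5 mentions no re-escalation, this corresponds to an event in cycle 7 that lowers cycle 8.

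**The case against.** The strongest reply is that 6.5 is naturally read drug by drug: whichever drug was held restarts one level lower. Elotuzumab has no levels, so for elotuzumab the clause does nothing. The elotuzumab-related row of Table 6-6, the mid-cycle rule in 6.6 and 6.6.2.1, and the permission to continue KRd in 6.6.2 all point the same way. Departures from the protocol's dose modifications go to the Lead Principal Investigator. This largely stands as the likely intent. It does not repair the text, because the Day 1 limb does not depend on any particular drug having been held. A site following either rule may also see no departure to report.

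The reply is also right about several stronger inferences that a reader might draw:
- That 6.5 requires both backbone drugs to be cut. It names none. Cutting both is one reading among several, and dexamethasone has levels too.
- That Table 6-6 always protects the partners when elotuzumab is held. It does so exactly in the one row for other elotuzumab-related toxicity. Rows for Grade 3 rash, Grade 2 to 3 allergic reaction, painful Grade 2 or Grade 3 neuropathy, and general drug-related toxicity hold or stop elotuzumab and also reduce, or allow reduction of, a partner.
- That the mid-cycle rules clash outright. Item 6-4 says "the treating investigator will decide if lenalidomide, carfilzominb, and/or dexamethasone will be held using recommended guidance for retreatment below", while 6.6 keeps the partners on schedule. But 6.6 also gives the investigator discretion to hold for treatment-related toxicity, which largely reconciles the two.
- That the problem is frequent. The documents give no rate of elotuzumab-only holds or Day 1 delays. Section 1.5.1.1 reports infusion reactions in about 10% of subjects in an earlier trial, with 5% needing interruption (median 25 minutes) and 1% discontinuing. Such reactions are mostly managed within the infusion or at the next dose. Those figures cover infusion reactions only, so they do not give the rate needed here.

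**Conclusion.** The point holds in a limited form. The 6.5 rule is wrong as written: for an elotuzumab-only toxicity it is empty or contradicts Table 6-6, and its Day 1 limb overrides or ignores restart doses that Tables 6-5 and 6-6 give for specific events. The effect is small. If a partner is reduced, one cycle loses 20% of its carfilzomib and/or 40% of its lenalidomide, which is 2.6% and 5.0% of the planned dose over cycles 1 to 8.

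A reader might quote a far larger loss: 7 x 42/1602 = 18.4% and 7 x 210/4200 = 35.0%. That needs an elotuzumab-only event in cycle 1, both partners reduced, and no re-escalation through cycle 8. Nothing in the documents suggests that this is typical, and it should be treated as a corner case.

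Nor do the documents support a claim of lost power or altered type I error. The test of 17 or more responders in 40 and the sample size in 10.2.1 do not depend on this rule, and no number of affected subjects can be given.

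**What to change.** In 6.5:
- Remove elotuzumab from the decrement trigger.
- State that the one-level decrement applies to carfilzomib and/or lenalidomide, whichever was held for, or is judged related to, the residual toxicity. Say explicitly that this includes unresolved Grade 2 toxicity.
- State that where a specific row of Table 6-5 or 6-6 gives a restart dose, that row governs.
- State that a hold or Day 1 delay due to elotuzumab toxicity alone leads to no decrement of the partner drugs.

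The Grade 2 wording matters. The residual rows of Table 6-6 begin at Grade 3, so limiting every decrement to what the tables already require would drop the reduction that 6.5 now provides for lingering Grade 2 carfilzomib or lenalidomide toxicity. Section 1.6 commits the trial to firm dose modification for anything above Grade 1.

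As an optional tidy-up, say in item 6-4 that the partners stay on schedule after a mid-cycle elotuzumab hold unless the tables, or the investigator's discretion under 6.6, require a hold.

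The cost is a few sentences of protocol wording through the amendment route in 13.4. Sample size, visits and the primary test do not change.
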